6.4 TOXICITY CRITERIA

The following adverse event management guidelines are intended to ensure the safety of each participant while on the study. The descriptions and grading scales found in the revised NCI Common Terminology Criteria for Adverse Events (CTCAE) version 4.0 will be utilized for AE reporting. All appropriate treatment areas should have access to a copy of the CTCAE version 4.0. A copy of the CTCAE version 4.0 can be downloaded from the CTEP web site (http://ctep.cancer.gov/protocolDevelopment/electronic_applications/ctc.htm).

7 NIH REPORTING REQUIREMENTS/DATA AND SAFETY MONITORING PLAN

7.1 DEFINITIONS

Please refer to definitions provided in Policy 801: Reporting Research Events found at: <https://irbo.nih.gov/confluence/pages/viewpage.action?pageId=36241835#Policies&Guidance-800Series-ComplianceandResearchEventReportingRequirements>.

7.2 OHSRP OFFICE OF COMPLIANCE AND TRAINING/ IRB REPORTING

7.2.1 Expedited Reporting

Please refer to the reporting requirements in Policy 801: Reporting Research Events and Policy 802 Non-Compliance Human Subjects Research found at:

<https://irbo.nih.gov/confluence/pages/viewpage.action?pageId=36241835#Policies&Guidance-800Series-ComplianceandResearchEventReportingRequirements>. Note: Only IND Safety Reports that meet the definition of an unanticipated problem will need to be reported per these policies.

7.2.2 IRB Requirements for PI Reporting at Continuing Review

Please refer to the reporting requirements in Policy 801: Reporting Research Events found at: <https://irbo.nih.gov/confluence/pages/viewpage.action?pageId=36241835#Policies&Guidance-800Series-ComplianceandResearchEventReportingRequirements>.

7.3 NCI CLINICAL DIRECTOR REPORTING

Problems expeditiously reviewed by the OHSRP in the NIH eIRB system will also be reported to the NCI Clinical Director/designee; therefore, a separate submission for these reports is not necessary.

In addition to those reports, all deaths that occur within 30 days after receiving a research intervention should be reported via email unless they are due to progressive disease.

To report these deaths, please send an email describing the circumstances of the death to [contact] within one business day of learning of the death.

7.4 INSTITUTIONAL BIOSAFETY COMMITTEE (IBC) REPORTING CRITERIA

7.4.1 Serious Adverse Event Reports to IBC

The Principal Investigator (or delegate) will notify IBC of any unexpected fatal or life-threatening experience associated with the use of PROSTVAC as soon as possible but in no event later than 7 calendar days of initial receipt of the information. Serious adverse events that are unexpected and associated with the use of the PROSTVAC, but are not fatal or life-threatening, must be reported to the NIH IBC as soon as possible, but not later than 15 calendar days after the investigator's initial receipt of the information. Adverse events may be reported by using the FDA Form 3500a.

7.4.2 Annual Reports to IBC

Within 60 days after the one-year anniversary of the date on which the IBC approved the initial protocol, and after each subsequent anniversary until the trial is completed, the Principal Investigator (or delegate) shall submit the information described below. Alternatively, the IRB continuing review report can be sent to the IBC in lieu of a separate report. Please include the IBC protocol number on the report.

7.4.3 Clinical Trial Information

A brief summary of the status of the trial in progress or completed during the previous year. The summary is required to include the following information:

- the title and purpose of the trial
- clinical site
- the Principal Investigator
- clinical protocol identifiers;
- participant population (such as disease indication and general age group, e.g., adult or pediatric);
- the total number of participants planned for inclusion in the trial; the number entered into the trial to date whose participation in the trial was completed; and the number who dropped out of the trial with a brief description of the reasons
- the status of the trial, e.g., open to accrual of subjects, closed but data collection ongoing, or fully completed,
- if the trial has been completed, a brief description of any study results.

7.4.4 Progress Report and Data Analysis

Information obtained during the previous year's clinical and non-clinical investigations, including:

- a narrative or tabular summary showing the most frequent and most serious adverse experiences by body system

- a summary of all serious adverse events submitted during the past year
- a summary of serious adverse events that were expected or considered to have causes not associated with the use of the gene transfer product such as disease progression or concurrent medications
- if any deaths have occurred, the number of participants who died during participation in the investigation and causes of death
- a brief description of any information obtained that is pertinent to an understanding of the gene transfer product's actions, including, for example, information about dose-response, information from controlled trials, and information about bioavailability.

7.5 NIH REQUIRED DATA AND SAFETY MONITORING PLAN

7.5.1 Principal Investigator/Research Team

The clinical research team will meet on a regular basis (approximately weekly) when participants are being actively treated on the trial to discuss each participant. Decisions about dose level enrollment and dose escalation if applicable will be made based on the toxicity data from prior participants.

All data will be collected in a timely manner and reviewed by the principal investigator or a lead associate investigator.

Events meeting requirements for expedited reporting as described in section [Error! Reference source not found.](#) will be submitted within the appropriate timelines.

The principal investigator will review adverse event and response data on each participant to ensure safety and data accuracy. The principal investigator will personally conduct or supervise the investigation and provide appropriate delegation of responsibilities to other members of the research staff.

8 SPONSOR PROTOCOL/SAFETY REPORTING

8.1 DEFINITIONS

8.1.1 Adverse Event

Any untoward medical occurrence in a participant or clinical investigation subject administered a pharmaceutical product and which does not necessarily have a causal relationship with this treatment. An adverse event (AE) can therefore be any unfavorable and unintended sign (including an abnormal laboratory finding), symptom, or disease temporally associated with the use of a medicinal (investigational) product, whether or not related to the medicinal (investigational) product (ICH E6 (R2))

8.1.2 Serious Adverse Event (SAE)

An adverse event or suspected adverse reaction is considered serious if in the view of the investigator or the sponsor, it results in any of the following:

- Death,
- A life-threatening adverse event (see section **8.1.3**)
- Inpatient hospitalization or prolongation of existing hospitalization
 - A hospitalization/admission that is pre-planned (i.e., elective or scheduled surgery arranged prior to the start of the study), a planned hospitalization for pre-existing condition, or a procedure required by the protocol, without a serious deterioration in health, is not considered a serious adverse event.
 - A hospitalization/admission that is solely driven by non-medical reasons (e.g., hospitalization for patient convenience) is not considered a serious adverse event.
 - Emergency room visits or stays in observation units that do not result in admission to the hospital would not be considered a serious adverse event. The reason for seeking medical care should be evaluated for meeting one of the other serious criteria.
- Persistent or significant incapacity or substantial disruption of the ability to conduct normal life functions
- A congenital anomaly/birth defect
- Important medical events that may not result in death, be life-threatening, or require hospitalization may be considered a serious adverse drug experience when, based upon appropriate medical judgment, they may jeopardize the patient or subject and may require medical or surgical intervention to prevent one of the outcomes listed in this definition.

8.1.3 Life-threatening

An adverse event or suspected adverse reaction is considered "life-threatening" if, in the view of either the investigator or sponsor, its occurrence places the patient or subject at immediate risk of death. It does not include an adverse event or suspected adverse reaction that, had it occurred in a more severe form, might have caused death. (21CFR312.32)

8.1.4 Severity

The severity of each Adverse Event will be assessed utilizing the CTCAE version 4.0.

8.1.5 Relationship to Study Product

All AEs will have their relationship to study product assessed using the terms: related or not related.

- Related – There is a reasonable possibility that the study product caused the adverse event. Reasonable possibility means that there is evidence to suggest a causal relationship between the study product and the adverse event.

Abbreviated Title: Prostvac-Nivo in prostate ca

Version Date: 01.10.2023

- Not Related – There is not a reasonable possibility that the administration of the study product caused the event.

8.2 ASSESSMENT OF SAFETY EVENTS

AE information collected will include event description, date of onset, assessment of severity and relationship to study product and alternate etiology (if not related to study product), date of resolution of the event, seriousness and outcome. The assessment of severity and relationship to the study product will be done only by those with the training and authority to make a diagnosis and listed on the Form FDA 1572 as the site principal investigator or sub-investigator. AEs occurring during the collection and reporting period will be documented appropriately regardless of relationship. AEs will be followed through resolution.

SAEs will be:

- Assessed for severity and relationship to study product and alternate etiology (if not related to study product) by a licensed study physician listed on the Form FDA 1572 as the site principal investigator or sub-investigator.
- Recorded on the appropriate SAE report form, the medical record and captured in the clinical database.
- Followed through resolution by a licensed study physician listed on the Form FDA 1572 as the site principal investigator or sub-investigator.

For timeframe of recording adverse events, please refer to section **6.1**. All serious adverse events recorded from the time of first investigational product administration must be reported to the sponsor.

8.3 REPORTING OF SERIOUS ADVERSE EVENTS

Any AE that meets protocol-defined serious criteria or meets the definition of Adverse Event of Special Interest that require expedited reporting must be submitted immediately (within 24 hours of awareness) to OSRO Safety using the CCR SAE report form. All SAE reporting must include the elements described in section **8.2**.

SAE reports will be submitted to the Center for Cancer Research (CCR) at: [contact] and to the CCR PI and study coordinator. CCR SAE report form and instructions can be found at: <https://ccrod.cancer.gov/confluence/display/CCRCRO/Forms+and+Instructions>

Following the assessment of the SAE by OSRO, other supporting documentation of the event may be requested by the OSRO Safety and should be provided as soon as possible.

8.4 SAFETY REPORTING CRITERIA TO THE PHARMACEUTICAL COLLABORATORS

All events listed below must be reported in the defined timelines to [contact].

The CCR Office of Sponsor and Regulatory Oversight (OSRO) will send all reports to the manufacturer as described below.

Abbreviated Title: Prostvac-Nivo in prostate ca

Version Date: 01.10.2023

8.4.1 Bavarian-Nordic

To be sent by Office of Sponsor and Regulatory Oversight (OSRO), CCR, NCI

The Investigator should complete and submit an SAE Medwatch 3500 Form or an CCR SAE report form to OSRO containing all information that is required by the Regulatory Authorities, to BNIT by e-mail within 24 to 48 hours of awareness for SAEs deemed to be possibly, probably or definitely related to the study vaccines.

The SAE documentation, including the Medwatch 3500 Form or CCR SAE report form and available source records, should be emailed to:

Bavarian-Nordic, Inc.

Email: [contact]

[REDACTED]

The following minimum information is required:

- Study number/IIT regulatory identifier
- Subject number, sex and age
- The date of report
- A description of the SAE (event, seriousness of the event)
- Causal relationship to the study drug

Follow-up information for the event should be sent within 7 days as necessary.

SAEs that are deemed unrelated or unlikely to be due to the study vaccines are submitted regularly to BNIT at the following address:

Bavarian-Nordic, Inc.

Email: [contact]

[REDACTED]

8.4.2 Bristol-Myers-Squibb

To be sent by OSRO, CCR, NCI, NIH:

Following the subject's written consent to participate in the study, all SAEs, whether related or not related to study drug, must be collected, including those thought to be associated with protocol-specified procedures. All SAEs must be collected that occur within 100 days of discontinuation of dosing.

All SAEs must be collected that occur during the screening period. If applicable, SAEs must be collected that relate to any protocol-specified procedure (e.g., a follow-up skin biopsy). The investigator should report any SAE that occurs after these time periods that is believed to be related to study drug or protocol-specified procedure.

SAEs, whether related or not related to study drug, and pregnancies must be reported to BMS within 24 hours. SAEs must be recorded on BMS or an approved form; pregnancies on a Pregnancy Surveillance Form.

SAE Email Address: [contact]

Abbreviated Title: Prostvac-Nivo in prostate ca

Version Date: 01.10.2023

SAE [contact]

If only limited information is initially available, follow-up reports are required. (Note: Follow-up SAE reports should include the same investigator term(s) initially reported.)

If an ongoing SAE changes in its intensity or relationship to study drug or if new information becomes available, a follow-up SAE report should be sent within 24 hours to the BMS (or designee) using the same procedure used for transmitting the initial SAE report.

All SAEs should be followed to resolution or stabilization.

The Investigator will ensure that all SAEs in the clinical database are reported to BMS and any applicable health authority during the conduct of the study. This reconciliation will occur at least quarterly and be initiated by the investigator. Investigator will request a reconciliation report from: [contact]. During reconciliation, any events found to not be reported previously to BMS must be sent to [contact].

BMS will be provided with a simultaneous copy of all adverse events filed with the FDA.

SAEs should be reported on MedWatch Form 3500A, which can be accessed at: <http://www.accessdata.fda.gov/scripts/medwatch/> or CCR SAE report form.

All SAEs should simultaneously be faxed or e-mailed to BMS at:

Global Pharmacovigilance & Epidemiology

Bristol-Myers Squibb Company

[contact]

Email: [contact]

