3.3 DOSE MODIFICATIONS

Participants must have recovered to \leq grade 1 attributable toxicity for the parameters used to assess levels of organ function required for eligibility (see Section 2.1) after each treatment in order to receive a subsequent treatment. Participants who experience irAE may continue PROSTVAC alone if irAE appears to be driven by nivolumab. In such circumstances, investigator will discuss fully the potential risks with the participant and document that conversation appropriately. Any dosing interruption lasting > 6 weeks from the last dose will require participants to be removed from protocol with the following exceptions:

- Dosing interruptions to allow for prolonged steroid tapers to manage drug-related adverse events are allowed. Tumor imaging assessments should continue as per protocol even if dosing is interrupted
- Dosing interruptions > 6 weeks from the last dose that occur for non-drug-related reasons may be allowed
- For subjects with mCRPC who have stopped receiving nivolumab because of grade 3 or higher irAEs, nivolumab could be re-started if the participant had partial response according Prostate Cancer Working Group 3 (PCWG 3) and RECIST 1.1 criteria but subsequently develops PSA progression (by PCWG 3) while on PROSTVAC alone.

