⁵To be obtained within 8 weeks prior to start of enrollment

⁶To be obtained within 4 weeks prior to start of enrollment

⁷Restaging visits only

⁸Per PI discretion. For example, participants who have had a complete response to treatment may have the interval between re-staging imaging increased to 1 year. Research samples for these participants will also be collected yearly with staging.

⁹ Assessment of SAEs at approximately 100 days (\pm 1 week) after nivolumab discontinuation. Assessment may be conducted by phone if the participant cannot come to the NIH. Assessments may also be performed by a local provider.

Abbreviated Title: Prostvac-Nivo in prostate ca
Version Date: 01.10.2023

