3.7 CRITERIA FOR REMOVAL FROM PROTOCOL THERAPY AND OFF STUDY CRITERIA

Prior to removal from study, effort must be made to have all subjects complete a safety visit approximately 4-5 weeks for Lead-in mCRPC cohort and 6-8 weeks for neoadjuvant cohort) following the last dose of study therapy and at approximately 100 days after nivolumab discontinuation for both cohorts.

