6 DATA COLLECTION AND EVALUATION

6.1 DATA COLLECTION

The PI will be responsible for overseeing entry of data into a 21 CFR Part 11- compliant data capture system provided by the NCI CCR and ensuring data accuracy, consistency and timeliness. The principal investigator, associate investigators/research nurses and/or a contracted data manager will assist with the data management efforts. Primary and final analyzed data will have identifiers so that research data can be attributed to an individual human subject participant.

All adverse events, including clinically significant abnormal findings on laboratory evaluations, regardless of severity, will be followed until return to baseline or stabilization of event.

Document AEs from the first study intervention, Study Day 1, through 30 days after the subject received the last study drug administration. Beyond 30 days after the last study drug and through approximately 100 days, only adverse events which are serious and related to the study intervention need to be recorded.

An abnormal laboratory value will be recorded in the database as an AE **only** if the laboratory abnormality is characterized by any of the following:

- Results in discontinuation from the study
- Is associated with clinical signs or symptoms
- Requires treatment or any other therapeutic intervention

Abbreviated Title: Prostvac-Nivo in prostate ca

Version Date: 01.10.2023

- Is associated with death or another serious adverse event, including hospitalization.
- Is judged by the Investigator to be of significant clinical impact

If any abnormal laboratory result is considered clinically significant, the investigator will provide details about the action taken with respect to the test drug and about the participant's outcome.

End of study procedures: Data will be stored according to HHS, FDA regulations and NIH Intramural Records Retention Schedule as applicable.

Loss or destruction of data: Should we become aware that a major breach in our plan to protect subject confidentiality and trial data has occurred, this will be reported expeditiously per requirements in section **7.2.1**.

- Eligible participants must be confirmed and checklist completed. Consent form must be signed prior to registration with Central Registration Information Services.

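### The only 100-day SAE contact is timed from the last nivolumab dose, so men who continue PROSTVAC alone have no scheduled contact late in the post-drug recording window of section 6.1

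*Combined protocol and SAP*

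**What the plan says.** **Recording window.** Section 6.1 records all adverse events "through 30 days after the subject received the last study drug administration". After that it narrows what has to be entered: "Beyond 30 days after the last study drug and through approximately 100 days, only adverse events which are serious and related to the study intervention". Section 8.2 sends the reader to 6.1 for the recording period, so 6.1 governs. Section 8.4.2, on reporting to the nivolumab supplier, has its own sentence: "All SAEs must be collected that occur within 100 days of discontinuation of dosing". It does not name the drug.

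**Contact meant to serve the window.** Section 3.7 asks for two steps before a man leaves the study. One is a safety visit after the last dose of study therapy, at 4-5 weeks in CRPC and 6-8 weeks in the neoadjuvant cohort. The other is a contact "at approximately 100 days after nivolumab discontinuation for both cohorts". Footnote 9 of 3.5.1 and footnote 4 of 3.5.2 repeat the second step, give it a margin of one week either way, and allow it by phone.

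**Route by which the two agents end at different times.** Section 3.3 provides: "Participants who experience irAE may continue PROSTVAC alone if irAE appears to be driven by nivolumab". For the CRPC cohort it also describes a man who "subsequently develops PSA progression (by PCWG 3) while on PROSTVAC alone", so a vaccine-only period is foreseen. In that cohort PROSTVAC-F continues every 4 weeks until intolerance or progression.

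**The concern.** Section 3.7 uses two reference points in one sentence, the last study therapy for the safety visit and nivolumab for the 100-day contact, so they cannot be read as synonyms. The window in 6.1 starts from the last study drug. When PROSTVAC outlasts nivolumab, the contact falls early in that window or before it opens.

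Nothing else is scheduled to fill the remainder. After the safety visit, section 3.8 continues follow-up only for unresolved grade 3-4 events, and section 3.9 makes long-term follow-up optional. A man whose 100-day contact took place while he was still on vaccine has met both steps of 3.7 once the safety visit is done.

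Safety is the primary objective of the 10-man lead-in cohort and a secondary objective in localized disease. Without a scheduled question late in the window, a blank SAE record cannot be told apart from a question never asked. The men concerned have, by the terms of 3.3, already had an immune-related event.

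**Working it through.** No sample size, power or error rate in the plan depends on this, so there is no stated figure to reproduce. The check is calendar arithmetic.

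**Inputs**
- Length of the window: 100 days from the last study drug (6.1).
- Contact: 100 days from the last nivolumab dose, nominal (3.5.1, 3.5.2, 3.7).
- Safety visit: day 28-35 after the last study drug in CRPC, day 42-56 in the neoadjuvant cohort (3.7, 3.8).
- g: days from the last nivolumab dose to the last PROSTVAC dose.

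**Formulas**
- Contact day, counted from the last study drug = 100 − g.
- Days at the end of the window with no scheduled contact = 100 − max(100 − g, safety-visit day).

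**CRPC cohort**

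| g (days) | Contact day | Last scheduled contact | Days left |
|---|---|---|---|
| 0 | 100 | day 100 | 0 |
| 28 | 72 | day 72 | 28 |
| 56 | 44 | day 44 | 56 |
| 84 | 16 | safety visit, day 28-35 | 65-72 |
| 100 | 0 | safety visit, day 28-35 | 65-72 |

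The loss is capped by the safety visit: 100 − 35 = 65 and 100 − 28 = 72. The cap is reached once g is 65 to 72 days. From g = 100 the contact falls on or before the last PROSTVAC dose and contributes nothing to the window.

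Illustration (assumed dates): nivolumab ends at week 10 and PROSTVAC-F at week 52. The contact falls at week 10 + 100/7 = week 24.3, during treatment. Here g = (52 − 10) × 7 = 294 days, and 65 to 72 days are left after the safety visit.

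**Neoadjuvant cohort**

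Nivolumab is planned at weeks 2, 4, 6 and 8, and the last PROSTVAC-F at week 8. The largest nominal g is therefore (8 − 2) × 7 = 42 days.

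| Last nivolumab | g (days) | Contact day | Days left |
|---|---|---|---|
| week 8 | 0 | 100 | 0 |
| week 6 | 14 | 86 | 14 |
| week 4 | 28 | 72 | 28 |
| week 2 | 42 | 58 | 42 |

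In the last row the contact comes 58 − 56 = 2 days after the safety-visit window closes, so it adds little to that visit.

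**After re-anchoring.** If the contact is timed from the later of the two last doses, it falls on day 100, plus or minus 7, for every value of g. The nominal gap is 0.

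**The case against.** The strongest reply is that the nivolumab anchor may be deliberate. A CRPC man who stays on PROSTVAC remains in the two-weekly on-treatment column of the calendar, with history, examination and laboratory tests. The 100 days after nivolumab are therefore largely covered. In the illustration, the uncovered days begin more than 42 weeks after the last nivolumab dose and are post-vaccine days. Section 3.9 regards the pox vectors as carrying little risk of delayed events. This limits the harm, but it does not remove the mismatch, because 6.1 chose the last study drug as its anchor and the schedule does not follow it.

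Several stronger readings are tempting, and the documents do not support them:
- **That these men go unassessed throughout the window.** The safety visit lies inside it. The neoadjuvant calendar also has a visit about one week after final immunotherapy, and for shorter gaps the early contact falls inside the window too.
- **That the highest-risk men lose their nivolumab follow-up.** The on-treatment visits above argue against this. Section 3.7.1 also takes some men with severe or unresolved toxicity off treatment altogether.
- **That 8.4.2 proves the conflict.** In the nivolumab supplier's section, dosing may mean nivolumab dosing, which would agree with the calendars. The vaccine supplier's section has no 100-day window.
- **That restarting nivolumab makes matters worse.** A restart moves its final discontinuation later and tends to close the gap.
- **That a contact on day 93 breaches the plan.** Section 6.1 says approximately 100 days, and a one-week margin fits that.
- **That the trial undertakes to report 100-day SAE coverage.** Section 10 specifies no such analysis.

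It is also fair to say that SAEs can be reported without a scheduled contact, and that 8.4.2 asks for related SAEs even after its window.

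**Conclusion.** The point holds in limited form. The recording window in 6.1 and the contact meant to serve it start from different events, and 3.3 lets those events separate. For men who continue PROSTVAC alone, the later part of the window has no scheduled SAE contact: up to 65-72 of 100 days in CRPC and up to about 42 days in the neoadjuvant cohort.

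These figures assume nominal visit dates, a safety visit held on schedule after the last study drug, and no voluntary enrolment in long-term follow-up. The CRPC maximum needs PROSTVAC to outlast nivolumab by at least 65 to 72 days. The documents do not say how often men continue PROSTVAC alone. With planned cohorts of 10 and 17, the number is likely to be small. Men who stop both agents together are unaffected, and neither the lead-in decision rule nor the primary T-cell comparison in section 10 depends on this.

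**What to change.** In 3.5.1 footnote 9, 3.5.2 footnote 4 and 3.7, time the existing SAE contact at approximately 100 days, plus or minus one week, after the last dose of PROSTVAC or nivolumab, whichever is later. This matches 6.1. State the same anchor in 8.4.2 so that its reference to dosing is no longer open to two readings.

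This changes only when safety information is sought. The treatment provisions in 3.3 are untouched. The cost is a wording change in four places and a later phone call for the few men who stop the two agents at different times. For everyone else the call stays on the same day.
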